**REMISSION OR LOW DISEASE ACTIVITY TABLE OF EVENTS WITH FLARE**

Procedure	Screening Period	DAY 1	WEEK 2	MONTH 1,2,3,4,5	MONTH 6/ET	FLARE	EVERY 4 WEEKS	FOLLOW-UP (WEEK 48-52)
Medication review	X	X	X	X		X	X	X
Review of side effects	X	X				X		
Physical examination	X	X			X	X		
Height (screening only) & weight	X	X		X	X	X	X	
Blood sample(s) (Approx.166-176 - ml, or - 12 tablespoons per visit )	X	X		X	X	X	X	
Urine sample	X	X		X	X	X	X	
Pregnancy test for women who can become pregnant	X	X		X	X	X	X	
Vital signs (temperature, blood pressure, heart rate (pulse))	X	X		X	X	X	X	
Assessments of your tender and swollen joints	X	X		X	X	X	X	
Assessments of disease activity	X	X		X	X	X	X	
Your Assessment of pain	X	X		X	X	X	X	
Rapid 3 patient questionnaire	X	X		X	X	X	X	
Abatacept infusion		X	X	X		X	X	
Adverse events		X		X	X	X	X	X

**REMISSION OR LOW DISEASE ACTIVITY TABLE OF EVENTS**

Procedure	Screening Period	DAY 1	WEEK 2	MONTH 1, 2, 3,4,5	MONTH 6/ET	MONTH 9	FOLLOW-UP (WEEK 48-52)
Medication review	X	X	X			X	X
Review of side effects	X	X					
Physical examination	X	X			X		
Height (screening only) & weight	X	X	X	X	X		
Blood sample(s) (Approx.166-176 - ml, or - 12tablespoons per visit)	X	X	X	X	X	X	
Urine sample	X	X	X	X	X		
Pregnancy test for women who can become pregnant	X	X	X	X			
Vital signs (temperature, blood pressure, heart rate (pulse))	X	X	X	X	X		
Assessments of your tender and swollen joints	X	X	X	X	X	X	
Assessments of disease activity	X	X	X	X	X	X	
Your Assessment of pain	X	X	X	X	X	X	
Rapid 3 patient questionnaire	X	X	X	X	X		
Abatacept infusion		X	X	X			
Adverse events		X		X	X	X	X

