### 3 Study Design

#### 3.1 General Design

A phase IV open-label clinical trial in which each CCP/ACPA+ patient will be their own longitudinal control for the immunomodulatory activity of Abatacept. All patients will have blood collection, including for peripheral blood mononuclear cells (PBMC), PBMC RNA and plasma, at screening and at day 0 after which Abatacept will be initiated in concert with methotrexate or pre-existing csDMARD. Each patient will then be reevaluated at 3 months and 6 months. In all patients, Abatacept will be discontinued after 6 months. Patients who have flared or failed to achieve low disease activity at 6 months, will exit the trial except for one post study visit for lab work at 9 months.

In patients who have achieved low disease activity by DAS28-CRP (<3.2) or CDAI (<10), Abatacept will be held for 6 months or until a flare results. A flare is defined by an examination demonstrating a DAS28-CRP that is greater than an absolute value of 4.0) or a CDAI >15, both defining the mid-range of a moderate flare. Alternatively, a 30% increase in the absolute level of the DAS28-CRP or CDAI that result in measures of 3.2 and 10 respectively, will be considered evidence of a flare. If patients do not experience a flare after 6 months off Abatacept (by week 52) they will also exit the study after a final visit with an exit blood draw.

Overall, in this pilot study, patient screening will continue until 25 suitable patients are enrolled and started on therapy in the trial. We predict enrollment of 2-3 patients/month, and hence the study should be fully enrolled by month 14 with the expectation that 70-80% will achieve low disease activity at week 24 enabling 17-20

patients to be followed for flare following Abatacept dechallenge. This estimate is based on the observation that treat provides nearly 60% ACR 50 responses, despite the fact that patients were selected for evidence of erosive disease.

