#### **NON-RESPONDERS TABLE OF EVENTS**

Procedure	Screening Period	DAY 1	WEEK 2	MONTH 1, 2, 3,4,5	MONTH 6/ET	MONTH 9	FOLLOW-UP (WEEK 48-52)
Medication review	X	X	X			X	X
Review of side effects	X	X					
Physical examination	X	X			X		
Height (screening only) & weight	X	X	X	X	X		
Blood sample(s) (Approx.166-176 - ml, or - 12tablespoons per visit )	X	X	X	X	X	X	
Urine sample	X	X	X	X	X		
Pregnancy test for women who can become pregnant	X	X	X	X			
Vital signs (temperature, blood pressure, heart rate (pulse))	X	X	X	X	X		
Assessments of your tender and swollen joints	X	X	X	X	X	X	
Assessments of disease activity	X	X	X	X	X	X	
Your Assessment of pain	X	X	X	X	X	X	
Rapid 3 patient questionnaire	X	X	X	X	X		
Abatacept infusion		X	X	X			
Adverse events		X		X	X	X	X

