### 3.2 Primary Study Endpoints

To assess the efficacy of Abatacept + csDMARD to induce low disease activity [DAS28-CRP (<3.2) or CDAI (<10) that can be maintained on csDMARD alone. A necessary co-primary objective is the relationship between clinical response and changes in B cell and antibody parameters that are unaffected by TNF-inhibition.

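### For patients who have not flared, the schedule marks neither a disease-activity score nor the promised exit blood draw at Week 48-52

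*Combined protocol and SAP*

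**What the plan says.** Section 3.2 makes the primary endpoint the induction of low disease activity "that can be maintained on csDMARD alone". It names no time point; the horizon comes from section 3.1.

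Section 3.1 (General Design) says that in patients with low disease activity at 6 months, "Abatacept will be held for 6 months or until a flare results". The flare rule rests on a score: "A flare is defined by an examination demonstrating a DAS28-CRP" above 4.0, or a CDAI above 15. The alternative is "a 30% increase in the absolute level of the DAS28-CRP or CDAI" that brings the score to 3.2 or 10 respectively. Week 52 is the limit. For patients without flare by then, "they will also exit the study after a final visit with an exit blood draw".

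Three schedules follow: "NON-RESPONDERS TABLE OF EVENTS", "REMISSION OR LOW DISEASE ACTIVITY TABLE OF EVENTS WITH FLARE", and the one headed only "REMISSION OR LOW DISEASE ACTIVITY TABLE OF EVENTS", called the no-flare table below. In the no-flare table, joint counts, disease activity and blood samples are marked up to Month 9 and blank at Week 48-52. The visit-by-visit headings at the end of section 5 add no detail.

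**The concern.** Whether low disease activity was maintained off abatacept can be decided only by scoring the patient. If a site works from the no-flare table, the final visit consists of a medication review and adverse-event questions. A patient whose disease returned after Month 9, and who did not come in because of it, would leave the study with no score to show it and could be counted as a success. The error runs in one direction, towards maintenance.

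The exit blood draw is a separate problem. The text requires it and the table omits it, so a site following the table could miss the end-of-hold sample. If the draw is taken anyway, no score is scheduled alongside it. Yet the co-primary objective relates clinical response to B cell and antibody changes, and section 6.2 plans correlations between shifts in clinical activity and the antibody and memory B cell levels.

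**Working it through.** **1. Number entering the hold.** Section 3.1 expects 70-80% of 25 patients to reach low disease activity. 0.70 × 25 = 17.5 and 0.80 × 25 = 20, which agrees with the stated 17-20.

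**2. The no-flare table.** It has 14 rows and 7 visit columns, and the cell counts match the header, so no column has shifted in extraction. At Week 48-52, 2 of 14 rows are marked: medication review and adverse events. Joint counts, disease activity, pain and blood are blank.

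**3. Comparison with the non-responder table.** All marks are identical across the 14 rows and 7 columns. Non-responders leave the trial apart from one laboratory visit at 9 months, whereas held patients are followed to week 52. The likeliest explanation is that the table was not adapted to the hold.

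**4. Which table governs the hold.** The flare table has a FLARE column and an EVERY 4 WEEKS column. Both mark joint counts, disease activity and blood, and both also mark an abatacept infusion. Infusions during the hold would contradict section 3.1, so the natural reading is that these columns apply after a flare. This is an inference; the plan does not state it. On this reading a patient without flare has one scheduled score after Month 6, at Month 9, and none later.

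**5. Unscored part of the hold.** The hold starts at week 24 (section 3.3) and runs to week 52: 52 − 24 = 28 weeks. Month 9 is taken as week 36 to 39.
- Month 9 at week 39: 52 − 39 = 13 weeks; 13/28 = 46%.
- Month 9 at week 36: 52 − 36 = 16 weeks; 16/28 = 57%.
- Final visit at week 48 instead (24-week hold): 48 − 39 = 9 and 48 − 36 = 12 weeks; 9/24 = 38% and 12/24 = 50%.

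**6. Illustration of scale, on assumptions that are not in the plan.** Take a constant flare hazard, cumulative flare probability *p* over 28 weeks, and Month 9 falling *s* = 12 or 15 weeks into the hold. The share of flares that begin after Month 9 is [(1 − p)^(s/28) − (1 − p)] / p.
- p = 0.2: 0.54 (s = 12) or 0.44 (s = 15).
- p = 0.7: 0.42 (s = 12) or 0.32 (s = 15).

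For 17-20 patients this is about 1.5 (p = 0.2, s = 15, 17 patients) to 5.9 (p = 0.7, s = 12, 20 patients) flares beginning after the last scheduled score. Only those that prompt no visit would be missed, so these figures are ceilings under the assumptions.

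**The case against.** The strongest objection is that section 3.1 already implies the assessment. It defines flare by examination, sets week 52 as the limit and requires a final visit with blood taken; declaring a patient free of flare at that visit presupposes a score. This stands in part. The visit and the draw are in the plan, so for blood the fault is a mismatch between text and table. The score, however, is left to implication, and the table a site would work from omits it.

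Four stronger readings are tempting, and the documents do not support them.

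- *Both low-disease-activity tables share the defect.* The flare table's Week 48-52 column is equally bare, but those patients have already failed maintenance, and their flare is scored and sampled in the FLARE column. The blank there takes nothing from the endpoint.
- *The gap exists whichever table governs the hold.* If the 4-weekly visits covered the hold, they would fall at 24 + 6 × 4 = week 48 and 24 + 7 × 4 = week 52, each with joint counts, disease activity and blood. The concern therefore depends on the reading in step 4 of the check. The infusion marks favour that reading, but it remains an inference.
- *All 17-20 patients are affected.* That is a maximum. Patients who flare earlier have already reached their outcome.
- *The dechallenge hypothesis loses its key sample.* Section 2 ties reaccumulation of memory B cells to flare, and the flare draw is marked. Patients serve as their own controls, and those without flare also have a Month 9 sample.

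It is also fair to say that this is an exploratory pilot without a sample-size calculation, and that section 6.2 specifies no analysis of a maintenance proportion. No planned test is shown to change. That limits the consequence, but a primary endpoint still has to be measured, and the results are meant to inform the power of later studies.

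**Conclusion.** The concern holds for the no-flare table and should be fixed. Its Week 48-52 column omits the exit draw that section 3.1 requires, and no joint count or DAS28-CRP/CDAI is explicitly scheduled at that visit in text or table. If the flare table's FLARE and EVERY 4 WEEKS columns apply only after flare, about half of the hold (13-16 of 28 weeks, with Month 9 at week 36-39) follows the last scheduled score. A flare in that period that brings no visit could pass as maintenance. At most 17-20 patients are exposed. How many would be misclassified is unknown, because the plan gives neither a flare rate nor the chance that a flare prompts a visit.

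**What to change.** In the no-flare table, mark joint counts, DAS28-CRP/CDAI (with CRP) and the exit blood draw at the existing Week 48-52 visit for patients who have not flared. State that this table applies from Month 6 until flare, and that the flare table's FLARE and EVERY 4 WEEKS columns apply from the flare visit onward. More frequent scoring during the hold is optional.

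The cost is an amendment to the schedule and a longer final visit, with at most 17-20 added examinations. No visits are added. CRP can be run from the exit draw, so no draw is needed beyond the one section 3.1 already requires; the tables put a sampling visit at about 166-176 ml.

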## Study Summary

Title	Rheumatoid arthritis memory B cells and Abatacept
Short Title	RAMBA
Protocol Number	IM101-768
BMS Protocol Number	IM101-768
Phase	Phase 4
Methodology	Open label
Study Duration	12 months
Study Center(s)	Single-center
Objectives	We will test the hypothesis that ABATACEPT treatment influences the levels of circulating autoimmune anti-citrullinated protein antigen (ACPA) memory B cells are central drivers of pathogenesis.
Number of Subjects	25
Diagnosis and Main Inclusion Criteria	Adults with Seropositive (CCP or ACPA) Rheumatoid Arthritis who are Naive to Biologic Disease-Modifying Antirheumatic Drugs
Study Product, Dose, Route, Regimen	Abatacept Time 0, Week 2, Month 1, 2, 3, 4, & 5 IV administration on Abatacept (7 infusions)
Duration of administration	6 months with active therapy followed by holding Abatacept for 6 months or until flare occurs while concurrent MTX or csDMARDs are continued.
Reference therapy	
Statistical Methodology	We will assess whether ABATACEPT challenge that induces clinical benefits are paralleled by reductions (i.e.,normalization) in the in vivo representation of disease-associated anti-citrullinated protein antigen (ACPA) memory B cells, and circulating autoantibody levels after 6 months of treatment.

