### **1.5 Dose Rationale and Risk/Benefits**

Abatacept intravenous should be administered as a 30-minute intravenous infusion utilizing the weight range-based dosing specified below. Following the initial intravenous administration, an intravenous infusion should be given at 2 and 4 weeks after the first infusion and every 4 weeks thereafter for a total of 7 doses.

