#### Age and Reproductive Status

- a) Men and women, age's  $\geq 18$  years (or age of majority)
- b) Women of childbearing potential (WOCBP) must have a negative serum or urine pregnancy test (minimum sensitivity 25 IU/L or equivalent units of HCG) within 24 hours prior to the start of study drug.
- c) Women must not be breastfeeding and must agree not to breastfeed during the study and for 100 days thereafter
- d) WOCBP must agree to follow instructions for method(s) of contraception for the duration of treatment with study drug plus 5 half-lives of study drug (70 days) plus 30 days (duration of ovulatory cycle) for a total of 100 days post-treatment completion.
- e) Males who are sexually active with WOCBP must agree to follow instructions for

method(s) of contraception for the duration of treatment with study drug, plus 5 half-lives of the study drug (70 days) plus 90 days (duration of sperm turnover) for a total of 160 days post-treatment completion.

f) Azoospermic males and WOCBP who are continuously not heterosexually active are exempt from contraceptive requirements. However they must still undergo pregnancy testing as described in this section. Investigators shall counsel WOCBP and male subjects who are sexually active with WOCBP on the importance of pregnancy prevention and the implications of an unexpected pregnancy.

Investigators shall advise WOCBP and male subjects who are sexually active with WOCBP on the use of highly effective methods of contraception. Highly effective methods of contraception have a failure rate of < 1% when used consistently and correctly.

At a minimum, subjects must agree to use one highly effective method of contraception as listed below.

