### **4.4     *Early Withdrawal of Subjects***

#### **4.4.1   *When and How to Withdraw Subjects***

All subjects who have received at least one dose of study drug and exit the study early will complete an early termination (ET) visit at the time of study discontinuation. Subjects will continue standard of care appointments with their primary rheumatologist after ET visit.

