## Pregnancy

If, following initiation of the investigational product, it is subsequently discovered that a study participant is pregnant or may have been pregnant at the time of investigational product exposure, including during at least 5 half-lives after product administration, the investigational product will be permanently discontinued in an appropriate manner (e.g., dose tapering if necessary for participant).

The investigator must immediately notify [contact] of this event via either the CIOMS, MedWatch or appropriate Pregnancy Surveillance Form in accordance with SAE reporting procedures.

Protocol-required procedures for study discontinuation and follow-up must be performed on the participant.

Follow-up information regarding the course of the pregnancy, including perinatal and neonatal outcome and, where applicable, offspring information must be reported on the CIOMS, MedWatch, BMS Pregnancy Surveillance Form, or approved site SAE form. A BMS Pregnancy Surveillance Form may be provided upon request.

Any pregnancy that occurs in a female partner of a male study participant should be reported to BMS. Information on this pregnancy will be collected on the Pregnancy Surveillance Form. In order for Sponsor or designee to collect any pregnancy surveillance information from the female partner, the female partner must sign an informed consent form for disclosure of this information.

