  - Other important findings which may be reported by BMS as an Expedited Safety Report (ESR) include: increased frequency of a clinically significant expected SAE, an SAE considered associated with study procedures that could modify the conduct of the study, lack of efficacy that poses significant hazard to study subjects, clinically significant safety finding from a nonclinical (eg, animal) study, important safety recommendations from a study data monitoring committee, or sponsor decision to end or temporarily halt a clinical study for safety reasons.
  - Upon receiving an ESR from BMS, the investigator must review and retain the ESR with the IB. Where required by local regulations or when there is a central IRB/IEC for the study, the sponsor will submit the ESR to the appropriate IRB/IEC. The investigator and IRB/IEC will determine if the informed consent requires revision. The investigator should also comply with the IRB/IEC procedures for reporting any other safety information.
  - In addition to the Sponsor Investigator's responsibility to report events to their local HA, suspected serious adverse reactions (whether expected or unexpected) shall be reported by BMS to the relevant competent health authorities in all concerned countries according to local regulations (either as expedited and/or in aggregate reports).

SAEs, whether related or not related to study drug, and pregnancies must be reported to BMS within 24 hours \ 1 Business Day of becoming aware of the event. SAEs must be recorded on either CIOMS, MedWatch, or approved site SAEform.

Pregnancies must be reported and submitted to BMS on any of the following form(s):

1. MedWatch or, CIOMS or
2. BMS Pregnancy Surveillance Form or,
3. Approved site SAE form

**SAE Email Address:** [contact]

**SAE [contact]

If only limited information is initially available, follow-up reports are required. (Note: Follow-up SAE reports should include the same investigator term(s) initially reported.)

If an ongoing SAE changes in its intensity or relationship to study drug or if new information becomes available, a follow-up SAE report should be sent within 24 hours \ 1 Business Day to BMS using the same procedure used for transmitting the initial SAE report.

All SAEs should be followed to resolution or stabilization.

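### The three schedule tables conflict on pregnancy testing at Week 2 and Month 6/ET, and two of them schedule no test after the last infusion

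*Combined protocol and SAP*

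**What the plan says.** Section 3.1 of the combined protocol and SAP has three tables of events: one for non-responders, one for remission or low disease activity with flare, and one for remission or low disease activity without flare. All three have the row "Pregnancy test for women who can become pregnant".

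- The non-responders table and the no-flare table tick it at Screening, Day 1, Week 2 and Months 1 to 5. They leave it blank at Month 6/ET, Month 9 and Follow-up.
- The flare table ticks it at Screening, Day 1, Months 1 to 5, Month 6/ET, Flare and Every 4 Weeks. It leaves it blank at Week 2 and Follow-up.

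The General Design text puts every patient on the same course to Month 6. Only then do non-responders leave, while for patients in low disease activity "Abatacept will be held for 6 months or until a flare results". Section 1.5 gives infusions at 0, 2 and 4 weeks and "every 4 weeks thereafter for a total of 7 doses". Under Section 4.4.1, treated patients who leave early "will complete an early termination (ET) visit at the time of study discontinuation", and that visit shares the Month 6 column.

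Section 4.1 (Age and Reproductive Status) sets 5 half-lives at 70 days and requires one negative test within 24 hours before the first dose. The Pregnancy text in Section 7.1 covers exposure "including during at least 5 half-lives after product administration". Section 7.2.1 adds that "pregnancies must be reported to BMS within 24 hours" or one business day of awareness.

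**The concern.** A site needs one rule for each visit, and the tables give two. At Week 2 nobody knows whether a patient will respond. At Month 6 nobody knows whether a patient in low disease activity will later flare, and a later flare is all that separates the second and third tables. A patient who terminates early could be handled under any of them.

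What is at stake is participant safety, not inference. If the non-responders or no-flare table is followed, a woman who completes treatment has no laboratory test after her last dose, and a woman who leaves early has none at her exit visit. A pregnancy that she has not recognised could then pass through the exposure period without the prompt reporting that the protocol wants. If the flare table is followed, the Week 2 infusion is the only ticked infusion column without a test.

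**Working it through.** **Ticks per column** (14 rows in each table; the non-responders and no-flare tables are identical in these two columns):

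| Column | Non-responders and no-flare | Flare | Rows that differ |
|---|---|---|---|
| Week 2 | 11 | 2 (medication review, infusion) | 9 |
| Month 6/ET | 10 | 11 | 1 (pregnancy test) |

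The nine Week 2 rows are weight, blood, urine, pregnancy test, vital signs, joint counts, disease activity, pain and RAPID3. At Month 6/ET the pregnancy test stands alone. Neighbouring rows such as the urine sample carry the tick in all three tables, so a shifted column does not explain that difference.

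**Tests from Screening through Month 6:**

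- Non-responders and no-flare tables: 1 (Screening) + 1 (Day 1) + 1 (Week 2) + 5 (Months 1 to 5) = 8.
- Flare table: 1 + 1 + 5 + 1 (Month 6) = 8.
- With both visits ticked: 1 + 1 + 1 + 5 + 1 = 9.

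**Timing after the last dose:**

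- Infusions (Section 1.5): weeks 0, 2, 4, 8, 12, 16 and 20. That is 7, matching the Study Summary. The last is on 20 × 7 = day 140, the Month 5 visit, which is also the last tested visit in the two tables.
- Exposure period (Section 4.1): 140 + 70 = day 210, or week 30.
- Month 6, taken as 24 weeks from Section 3.3: 24 × 7 = day 168, which is 168 − 140 = 28 days after the last dose and inside the period.
- Month 9, assumed to be week 36 to 39: day 252 to 273, which is 112 to 133 days after the last dose and outside it.
- Follow-up at weeks 48 to 52: day 336 to 364, which is 196 to 224 days after the last dose and outside it.

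The definition of a month does not change the result. With calendar months, Month 6 falls about 30 days and Month 9 about 122 days after the last dose. With the last dose at week 20 and Month 6 at week 26, the gap is 42 days. In each case Month 6/ET is the only scheduled visit within 70 days for a completer under the two tables, and the number of tests scheduled in that period is 0.

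**Search for a tie-breaker.** Section 4.1 fixes only the pre-dose test. It also says that exempt and abstinent women must still be tested, but gives no on-study dates. The tables are the only schedule.

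**The case against.** The strongest reply is that nothing in the protocol is breached. After Screening, the non-responders and no-flare tables test at exactly the visits where drug is given, which is a coherent policy, and no dose is due at Month 6. The Pregnancy text applies once a pregnancy is discovered and orders no testing. Women must also use contraception for 100 days after treatment. All of this stands. A reader might infer that the protocol requires tests to the end of the 70 days and that the tables break that rule; no section says so.

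A reader might also infer that, without a test, detection rests on the patient volunteering the information. The documents do not support that. Section 7.1 (Recording of Adverse Events) obliges the investigator to ask at each contact, pregnancy must be handled as a serious adverse event, and all three tables tick adverse events and physical examination at Month 6/ET. What remains is narrower: questioning cannot reveal a pregnancy of which the patient is unaware.

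On Week 2, the flare table's blank looks like a largely dropped column and not a pregnancy rule. Its Day 1 and Month 1 tests are 28 days apart, the same interval as between later monthly tests, so the safety effect there is small. This is right, and it argues for repairing the whole column.

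Finally, the count of zero applies only to women followed under the two tables, and the documents do not say how many of the 25 subjects could become pregnant. Neither point resolves the conflict between the tables.

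**Conclusion.** The concern holds as an inconsistency between tables with a modest safety consequence. One row differs at Month 6/ET and nine differ at Week 2, on a course that all patients share, and no text says which table governs. Under two of the three tables, no laboratory pregnancy test is scheduled in the 70 days after the last infusion. For completers, the one scheduled visit in that period, 28 days after the dose, goes untested, and early terminators have no test at their ET visit.

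This rests on Month 6 being week 24 and Month 9 being week 36 to 39; the alternatives tried give the same answer. The number of women affected is unknown and could be anywhere from 0 to 25. No dosing decision after Month 5 under the two tables, no endpoint and no analysis depends on it. It should be corrected because the remedy is cheap and the flare table already contains the missing test.

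**What to change.** Tick the pregnancy test at Month 6/ET in the non-responders table and the no-flare table, to match the flare table. Correct the whole Week 2 column of the flare table, all nine rows including the pregnancy test, to match the other two.

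The cost is one table amendment and one more pregnancy test per woman of childbearing potential through Month 6 (9 instead of 8), so at most 25 tests. Blood and urine are already collected at Month 6/ET in all three tables. At Week 2, anyone who would have been handled under the flare table also gains the other eight procedures, including the blood and urine samples, at an infusion visit that already takes place. No visit is added and the statistical analysis is unchanged.

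The gain has limits. A Month 6 test looks back over the first 28 of the 70 days, and an ET test over the time up to that visit. Neither excludes a later conception.
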